The visit schedule upon initiation of treatment consists of a recurrence visit at presentation, a visit on Day 3 of treatment with caplacizumab, weekly visits during treatment with caplacizumab (starting 1 day after the last daily PE), and a recurrence FU visit 1 week after the end of treatment with caplacizumab. At these visits, information with regard to the TTP recurrence (presenting symptoms, duration, and outcome) and treatment choice will be collected as will safety information (including AEs, safety laboratory parameters, vital signs and physical examination), and determination of pharmacokinetic [PK], ADA, pharmacodynamic [PD] parameters (vWF:Ag and Ristocetin cofactor activity [RICO]), and disease-related markers (ADAMTS13 activity and Tnl).

In case of recurrent thrombocytopenia requiring re-initiation of daily PE during an ongoing recurrence period (see [Figure 1](#)), a new visit cycle is to be started, with a recurrence visit on the day of the new recurrence followed by all subsequent visits as indicated in [Table 5](#). An i.v. loading dose of caplacizumab needs to be administered prior to re-initiation of PE for the recurrence. All remaining visits of the original schedule are no longer applicable and are not to be performed.

Q6M visits that are scheduled within a recurrence period will not be held as assessments at such visits would be confounded by the concurrent recurrence. Treatment with caplacizumab may not be initiated for subjects who do not fulfil the caplacizumab treatment criteria. Hence, these subjects will be treated with standard of care only. The visit schedule in case of initiation of only standard of care treatment includes a recurrence visit at presentation and a recurrence FU visit at 30 days after end of daily PE (see [Table 6](#) for schedule of assessments).

Figure 1 - Study flow of study ALX0681-C302

M: month; Y : year

Treatment in case of recurrence:

Initiation of treatment with caplacizumab is for subjects with a clinical diagnosis of an episode of recurrent acquired TTP requiring initiation of daily PE treatment and who had a baseline visit.

Treatment with caplacizumab is not permitted for subjects who:

- Are pregnant or intend to get pregnant in the near future
- Have a history of a severe and/or serious hypersensitivity reaction to investigational medicinal product (IMP) in Study ALX0681-C301 or Study ALX0681-C302.

Standard of care treatment (per standard site practice) can include:

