2.1.3.5 Other efficacy endpoints

2.1.3.5.1 TTP-related events

TTP related event is defined as:

- TTP-related death,
- recurrence of TTP
- or reported major thromboembolic event [e.g., myocardial infarction, cerebrovascular accident, pulmonary embolism or deep venous thrombosis] based on SMQ based on the SMQ ‘Embolic and thrombotic events (arterial, venous, and vessel type unspecified and mixed arterial and venous)’.

2.1.3.5.2 Time to TTP-related events:

The time to TTP related event (in days) is defined as the date from screening/baseline visit to the date of the first TTP related event. Patients without an event during the ALX0681-C302 study are censored at the end of the study.

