2.1.3.5.4 Recurrence of aTTP

A recurrence of aTTP is defined as recurrent thrombocytopenia requiring initiation of daily plasma exchange (PE).

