2.1.4 Safety endpoints

The safety analysis will be based on the reported adverse events and other safety information, such as clinical laboratory data, vital signs and physical examination.

Observation period

The observation period will be divided into 2 non mutually exclusive periods: the on-study period and the recurrence period.

The on-study observation period is defined as the time from informed consent until the end of the study (defined as last protocol planned visit).

The recurrence period is from the start of the recurrence episode, defined as recurrent thrombocytopenia requiring initiation of daily PE, until the last recurrence follow-up visit of that episode. In case of treatment with the IMP, the recurrence period is divided into 2 epochs:

- the **treatment epoch** is defined as the time from the first administration of the IMP to the last administration of the IMP.
- the **residual treatment** epoch is defined as the time from the last administration of the IMP to the last administration of the IMP + 30 days.

The treatment-emergent adverse event (TEAE) period will include both treatment and residual treatment epochs.

In case treatment with the IMP is not initiated during the recurrence episode, there is no subdivision of the recurrence period into the treatment epoch and the residual treatment epoch. The adverse event occurring during that period are not identified as treatment-emergent adverse events.

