2.3.2 Recurrence population

All subjects in the ITO population who have experienced at least one recurrence in study ALX0681-C302. The recurrence population will be used for analysis of data collected during recurrence periods.

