2.4.4 Analyses of efficacy endpoints

All efficacy endpoints related to assessments on the Q6M FU visits will be analyzed using the ITO population. Summarization will be conducted on the total study population and by analysis group. For the group-wise analysis, the following groups will be considered:

- caplacizumab-treated: defined as subjects in the ITO population who have been randomized to caplacizumab in study ALX0681-C301, evaluated up to their first recurrence in the ALX0681-C302 trial;
- standard of care-treated, defined as subjects in the ITO population who have been randomized to placebo in study ALX0681-C301, evaluated up to their first recurrence in the ALX0681-C302 trial.

Subjects who had a recurrence during study ALX0681-C301 or between the Final (28 day) FU visit in study ALX0681-C301 and Screening/Baseline in study ALX0681-C302, will not be considered for the group-wise analyses.

All efficacy endpoints related to assessments during the recurrence period will be analyzed using the recurrence population. The effect of retreatment of caplacizumab on these endpoints will be evaluated. For the group-wise analysis the following groups are considered, unless otherwise specified:

- Treated with IMP: defined as subjects in the recurrence population who received caplacizumab in the ALX0681-C302 during a recurrence episode
- Not treated with IMP: defined as subjects in the recurrence population who did not receive caplacizumab in the ALX0681-C302 during a recurrence episode.

Of note, depending on the recurrence episode, the same subject can appear in both analysis groups.

Select sensitivity analyses may be planned to assess the effect of heterogeneity in the timings of the baseline visit between subjects. Unless specified otherwise, no missing data imputation will be applied, and all efficacy endpoints will be analyzed as observed.

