2.4.4.1 TTP-related events

The number and percentage of participants with TTP-related event as well as the number of such events, will be summarized. The total number and percentage of participants who have at least one of the TTP-related events will also be calculated.

For the ITO population, it will be after 12 months follow-up (M FU), 24M FU and 36M FU as well as a cumulative summary. For the Recurrence population, it will be during each recurrence period separately.

TTP-related events will be listed.

The time to the first TTP-related event will be summarized on the ITO population, using Kaplan-Meier (KM) estimates such as the median, 25% percentile and 75% percentile with associated 95% CIs, as well as the number of events and the number of censored observations. The KM estimates will also be presented graphically.

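### In the recurrence population, the TTP-related-event composite counts the recurrence that opens each period, so its first-period percentage is 100% in both IMP groups as written

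*SAP*

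**What the plan says.** - **The composite.** SAP 2.1.3.5.1 makes any one of three things a TTP-related event, and one of them is "recurrence of TTP". SAP 2.1.3.5.4 defines that component: "A recurrence of aTTP is defined as recurrent thrombocytopenia requiring initiation of daily plasma exchange (PE".
- **The population and the period.** SAP 2.3.2 admits "All subjects in the ITO population who have experienced at least one recurrence in study ALX0681-C302". SAP 2.1.4 says "The recurrence period is from the start of the recurrence episode, defined as recurrent thrombocytopenia requiring initiation of daily PE" and ends the period at the episode's last recurrence follow-up visit.
- **The summary.** SAP 2.4.4.1: "The total number and percentage of participants who have at least one of the TTP-related events will also be calculated". For the ITO population this is done at 12, 24 and 36 months and cumulatively. For the other population: "For the Recurrence population, it will be during each recurrence period separately".
- **The groups.** SAP 2.4.4 splits recurrence-period results by whether caplacizumab was given in C302 during the episode, noting that "depending on the recurrence episode, the same subject can appear in both analysis groups".
- **A re-initiation of daily PE in an ongoing period.** SAP 1.4: "a new visit cycle is to be started, with a recurrence visit on the day of the new recurrence". The visits left in the old cycle are dropped. Table 1 in SAP 2.5.4 dates an episode from its recurrence visit.
- **The thromboembolic component.** SAP 2.1.3.5.1 uses the standardized MedDRA query for embolic and thrombotic events with no term removed. The safety tables in SAP 2.4.5.1 use the same query but remove PT TTP.

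**The concern.** The event that puts a subject into the recurrence population, and that opens each recurrence period, is also a component of the outcome counted in that period. A percentage of subjects with at least one such event is then fixed before any outcome is observed.

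This matters because repeated use of caplacizumab is a stated objective, TTP-related events head the list of main endpoints in the protocol synopsis, and SAP 2.4.4 says that the effect of retreatment on recurrence-period endpoints will be evaluated. SAP 2.4.4.3 tabulates recurrence itself only for the ITO population. That leaves 2.4.4.1 as the one planned efficacy table of event proportions in which a further recurrence could be compared between the episode-level IMP groups.

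The wording looks like a carry-over. In the parent study (protocol 1.2.4) a similar composite was counted during study drug treatment and concerned recurrence of the presenting episode, so the presenting episode was not itself an event. Here the window opens with a recurrence, and no such distinction is made.

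**Working it through.** The plan gives no figure to reproduce: there is no sample size calculation, no test and no expected rate for this population. The check is on the definitions.

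**1. First recurrence period.** Composite percentage = subjects in the period with (TTP-related death OR recurrence OR major thromboembolic event) / subjects in the period. The recurrence component (2.1.3.5.4) and the period start (2.1.4) are the same event. No section excludes it or restricts the count to later events. The one boundary rule in the SAP, written for adverse events in 2.4.5.1, includes the start date. So the numerator equals the denominator: n/n = 100% for any n, overall and in each IMP group.

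**2. Later periods.** SAP 2.4.4.1 states no denominator.
- Subjects with that episode: again n/n = 100%.
- The whole recurrence population: period 2 gives the share of subjects with a second episode. If 10 to 40% have one (an assumption), the figure is 10 to 40%, but it describes who entered the period and not what happened in it.

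**3. A further recurrence inside an open period.** Two readings are possible.
- SAP 1.4 starts a new visit cycle with its own recurrence visit, and Table 1 dates an episode from that visit. This suggests a new episode.
- SAP 1.4 also places the event within an ongoing recurrence period, and 2.1.4 ends the period at the last follow-up visit of the episode. This leaves room for one episode that spans several cycles.

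On either reading the literal first-period percentage stays at 100%; only event counts change. Table 1 gives no end date for an interrupted cycle whose follow-up visit is not performed.

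**4. Why removing the index event is not enough.** Let r be the probability of a further recurrence in the open period and q that of a death or thromboembolic event, taken as independent. The documents give neither, so the ranges are assumptions: r from 10 to 40%, q of 0 or 10%.
- Index excluded and re-initiation credited to the interrupted period: 1 − (1 − r)(1 − q). With q = 0 this is r, so 10 to 40%. With q = 10% it runs from 1 − 0.9 × 0.9 = 19% to 1 − 0.6 × 0.9 = 46%.
- Index excluded but re-initiation only opens the next period: q alone, so 0 to 10%. The further recurrence is then an outcome of no period.

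**5. A second route for the index event.** Relapses and exacerbations must be reported as serious adverse events (protocol 3.4.9.1). In the phase II analysis in protocol 1.2.4, the same query counted TTP exacerbations as major thromboembolic events: 3 of 4 events with caplacizumab and 13 of 20 with placebo. Without the PT TTP exclusion in 2.1.3.5.1, the index recurrence could re-enter through the thromboembolic component even after it is removed from the recurrence component. It could also enter the thromboembolic table in 2.4.4.2.

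**The case against.** The best defence is that one row is empty and little else is lost. SAP 2.4.4.2 tabulates thromboembolic events by recurrence period with a breakdown by preferred term. SAP 2.4.5.1 counts participants with fatal adverse events by analysis period, 2.4.5.2 lists them, and 2.4.4.1 lists all TTP-related events and gives event counts. Protocol 3.6.4 plans the composite mainly at 12, 24 and 36 months. The outcomes that protocol 3.4.3 names for a recurrence (platelet response, PE duration, hospital and intensive care days) do not depend on the index event. No test is planned, and a row of 100% would be obvious. All of this stands, and it limits the impact. It does not make the rule correct: in a descriptive study the tables are the result, and dropping the index event would be left to whoever programs the table.

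A reader might infer more than the documents support:
- **That deaths and thromboembolic events are hidden.** They are not, for the reasons just given.
- **That a further recurrence is definitely moved into the next period.** This is the more natural reading of SAP 1.4 with Table 1, but 2.1.4 allows another. It is an ambiguity.
- **That every period must show 100%.** Later periods depend on an unstated denominator. Table 1 also starts at the recurrence visit and 2.1.4 at the event, so an index onset dated before the visit could fall outside the window. The visit is held at presentation, which limits this, and any resulting drop below 100% would reflect dating only.
- **That a contrast like the phase II exacerbation rates (8.4% versus 28.2%) is being erased.** Those arms were randomized. Under protocol 3.2.3, subjects go untreated here because of pregnancy or intended pregnancy, prior hypersensitivity or no baseline visit, so they are not a counterpart to a placebo arm.

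**Conclusion.** Wrong as written, with impact on descriptive tables only. Under the SAP's own definitions, the percentage with at least one TTP-related event in the first recurrence period is 100% in both IMP groups and carries no information about retreatment. This rests on two readings: nothing excludes the index recurrence, which the text bears out, and the event falls within the period it opens, as 2.1.4 defines it. For later periods the same result also requires subjects with that episode as the denominator. How a further recurrence is attributed is unresolved in the SAP, and that choice decides whether the corrected composite can show one at all. The missing PT TTP exclusion is a real gap, but how often the index event would enter that way cannot be known from the documents.

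**What to change.** In SAP 2.4.4.1, for the recurrence population:

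1. Exclude the index recurrence. Count only TTP-related death, major thromboembolic events and further recurrences with onset after the start of the episode.
2. Credit a re-initiation of daily PE during an ongoing recurrence period to the period it interrupts. End that period for analysis on the date of the new recurrence, that date included. The same recurrence may open the next episode, where it is the excluded index event.
3. Use subjects with that recurrence episode as the denominator, overall and by IMP group.
4. In 2.1.3.5.1, remove PT TTP from the thromboembolic query, as 2.4.5.1 already does. Table 2.4.4.2 then follows the same definition.

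The cost is SAP wording plus the derivation rules for the index flag, the end date of an interrupted cycle, the denominator and the term list. No new data are needed.

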2.4.4.2 Major thromboembolic events

The number and percentage of participants with a major thromboembolic event as well as the number of such events, will be summarized. The total number and percentage of participants who have at least one of major thromboembolic event will also be calculated. Within the major thromboembolic events category, the frequency tabulation of PTs will also be summarized.

For the ITO population, it will be after 12M FU, 24M FU and 36M FU as well as a cumulative summary. For the Recurrence population, it will be during each recurrence period separately.

The time to the first major thromboembolic event will be summarized on the ITO population, using Kaplan-Meier (KM) estimates such as the median, 25% percentile and 75% percentile with associated 95% CIs, as well as the number of events and the number of censored observations. The KM estimates will also be presented graphically.

2.4.4.3 Recurrence of TTP

The number and percentage of participants with a recurrence of TTP as well as the number of such events, will be summarized over time for the ITO population (after 12M FU, 24M FU and 36M FU).

Time to the first recurrence of TTP will be summarized on the ITO population, using Kaplan-Meier (KM) estimates such as the median, 25% percentile and 75% percentile with associated 95% CIs, as well as the number of events and the number of censored observations. The KM estimates will also be presented graphically.

A subgroup analysis of incidence of recurrence of TTP to ADAMTS13 levels ($\geq 10\%$, $< 10\%$) after end of previous TTP episode in the ALX0681-C301 trial will be performed on the ITO population.

2.4.4.4 TTP recurrence information.

TTP recurrence information will be summarized for the recurrence population.

2.4.4.4.1 Presenting symptoms

The number and percentage of participants with presenting symptoms at the recurrence visit will be summarized for each recurrence episode. The denominator for the percentage calculation is the number of assessable participants at each time point.

2.4.4.4.2 Duration of TTP (time to platelet count response)

The duration of TTP (platelet count response), will be summarized for each recurrence episode. The denominator for the percentage calculation is the number of assessable participants at each time point.

2.4.4.4.3 Outcome of recurrence episode

The outcome of the recurrence at the recurrence follow-up visit will be summarized for each recurrence episode. The denominator for the percentage calculation is the number of assessable participants at each time point.

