^a Pregnancy test (urine or blood) for female subjects of childbearing potential will be assessed per local laboratory.

^b TTP recurrence information includes presenting symptoms (assessed at recurrence visit), duration (assessed at the Week 1 visit) and outcome (assessed at the recurrence FU visit).

^c Heart rate and blood pressure to be assessed after 5 min in supine position.

^d To be assessed at the post-daily PE Day 29 only.

** Treatment with caplacizumab may not be initiated for subjects who do not fulfil the caplacizumab treatment criteria. These subjects will be treated with standard of care only. For the Schedule of Assessments, please refer to [Appendix 1](#).

-
- ^e Clinical laboratory analyses include hematology (Hb, Hct, RBC, WBC, platelets); chemistry (AST, ALT, LDH, creatinine, protein, cholesterol and CRP). Urinalysis includes assessment of albumin. The results of assessment of platelet count and LDH levels performed as per standard of care (by a local laboratory) at any time during the recurrence period will be collected in the eCRF, if available.
- ^f At the recurrence visit and the Treatment Day 3 visit, samples need to be collected prior to start of the PE treatment and/or study drug administration (whatever comes first). At all subsequent visits, blood samples need to be taken prior to study drug administration.
- ^g In case of a severe and/or serious hypersensitivity reaction, an additional blood sample to characterize the reaction should be collected as soon as possible after the start of the event.
- ^h PD parameters include RICO and vWF:Ag.

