3.4.1.3. RECURRENCE PERIOD

Upon recurrence of TTP, defined as recurrent thrombocytopenia requiring initiation of daily PE, standard of care treatment consisting of daily PE and immunosuppression is to be initiated. In addition, open-label caplacizumab will be administered daily for the duration of daily PE and for 30 days thereafter. Treatment with caplacizumab may be extended for a maximum of 4 weeks in case of persistent signs and symptoms of underlying disease activity (e.g., ADAMTS13 activity profile remains below 10% based on weekly measurements).

The visit schedule upon initiation of treatment consists of a recurrence visit at presentation, a visit on Day 3 of treatment with caplacizumab, weekly visits during treatment with caplacizumab (starting 1 day after the last daily PE), and a recurrence FU visit 1 week after the end of treatment with caplacizumab. Q6M visits that are scheduled within a recurrence period will not be held as assessments at such visits would be confounded by the concurrent recurrence.

In case of recurrent thrombocytopenia requiring re-initiation of daily PE during an ongoing recurrence period (see [Figure 4](#) and [Table 2](#)), a new visit cycle is to be started, with a recurrence visit on the day of the new recurrence followed by all subsequent visits as indicated in [Table 2](#). All remaining visits of the original schedule are no longer applicable and are not to be performed.

If the new recurrence visit coincides with a visit of the original recurrence visit schedule, then assessments already performed for the original recurrence visit do not need to be repeated for the new recurrence visit.

Assessments will include (also see [Schedules of Assessments](#)):

- Review of caplacizumab treatment criteria (at the recurrence visit only)
- Pregnancy test (blood or urine) for female subjects of childbearing potential (Note: pregnancy is an exclusion criterion for treatment with caplacizumab)
- TTP recurrence information (at the recurrence visit, the Week 1 visit and the recurrence FU visit only)
- Concomitant medication
- PE information (at the Week 1 visit only)
- Study drug administration
- Quality of life assessment: SF36 questionnaire (at the recurrence FU visit only)
- Adverse events

- Clinical laboratory analyses include hematology (Hb, Hct, RBC, WBC, platelets) and chemistry (AST, ALT, LDH, creatinine, protein, cholesterol and CRP). Urinalysis includes assessment of albumin.
- Physical examination, vital signs

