9. APPENDIX

Appendix 1: Schedule of Assessments in Case of TTP Recurrence (in Case Treatment With Caplacizumab is not Initiated)

Study Period	Recurrence Period (no caplacizumab)	
	Recurrence Visit Recurrence Day 1	Recurrence FU visit 30 days after end of daily PE
TTP recurrence information ^a	X	X
PE information		X
Concomitant medication		→
Adverse events		→
Supine heart rate & blood pressure ^b	X	X
Physical examination	X	X
SF-36		X
Clinical laboratory analyses + urinalysis ^c	X	X
Organ damage markers: TnI ^d	X	X
ADAMTS13 activity ^d	X	X
Immunogenicity (ADA panel) ^d	X	
PD parameter : vWF:Ag ^d	X	X

^a TTP recurrence information includes presenting symptoms (assessed at recurrence visit), duration and outcome (assessed at the recurrence FU visit).

^b Heart rate and blood pressure to be assessed after 5 min in supine position.

[figure not shown]
^c Clinical laboratory analyses include hematology (Hb, Hct, RBC, WBC, platelets); chemistry (AST, ALT, LDH, creatinine, protein, cholesterol and CRP). Urinalysis includes assessment of albumin. The results of assessment of platelet count and LDH levels performed as per standard of care (by a local laboratory) at any time during the recurrence period will be collected in the eCRF, if available.

^d Samples need to be collected prior to start of the first PE treatment.

Signature Page

This is a representation of an electronic record that was signed electronically in Livelink.
This page is the manifestation of the electronic signature(s) used in compliance with the organizations
electronic signature policies and procedures.

Date: [Redacted]

Meaning: Approved

=====

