1.3 DETERMINATION OF SAMPLE SIZE

The sample size is not based on statistical considerations but rather on the number of subjects who complete Study ALX0681-C301 (HERCULES) and accept the option to participate in this FU study (ALX0681-C302). All subjects who enrolled in this FU study will be included in the safety and efficacy analyses.

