2.1.3.1.2 Duration of the TTP recurrence

The duration of TTP recurrence in days (time to platelet count response) is defined as initial platelet count $\geq 150 \times 10^9/L$ with subsequent stop of daily PE within 5 days. The start and end date time of the recurrence, for the calculation of the duration of TTP recurrence, are captured in the eCRF. There will be no imputation of missing data.

2.1.3.1.3 Outcome of the TTP recurrence:

The outcome of the TTP recurrence is assessed at the recurrence follow-up visit and is collected in the eCRF.

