2.4 STATISTICAL METHODS

For continuous parameters, descriptive statistics will be presented when $n \geq 2$. When $n = 1$, only sample size (n) and mean, i.e. the value itself, are shown. Descriptive statistics will include the number of non-missing data points (n), the arithmetic mean, the standard deviation (SD) (for baseline summaries) or standard error (SE) (for post-baseline, change from baseline, or percentage change summaries), the median, minimum and maximum.

For categorical parameters, frequency tabulations are prepared, consisting of frequency counts (non-missing observations) and percentages. Missing values will not be included in the denominator count when computing percentages.

Descriptive statistics of PK concentrations and PD data will additionally include 5% and 95% percentiles, SD of arithmetic mean, coefficient of variation (CV)% of arithmetic mean, geometric mean and geometric SD.

For the graphs showing mean values or percentages, an SE flag will be shown. For PK graphs showing geometric mean values, a geometric SD flag will be shown.

- Change from baseline and percentage change from baseline
- The change from baseline will be calculated for all post-baseline time points as:
- Change from baseline at time point $t = \text{value at time point } t - \text{baseline value}$.
- Percentage change from baseline at time point $t = 100 * \frac{[\text{value at time point } t - \text{baseline value}]}{\text{baseline value}}$.
- Change from baseline and percentage change from baseline will be calculated separately for each of the analysis periods from their respective baseline values.

Relative number of days

The relative day (DY) is calculated as follows:

- Visit date – reference date + 1 day, when the visit date is on or after the reference date
- Visit date – reference date, when the visit date is before the reference date.

The reference date is the date of first intake of the study drug, which by definition has DY=1. There is no DY=0.

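### In caplacizumab-treated recurrences, restarting daily PE cancels the only visit that records outcome, so the SAP's outcome table leaves out courses that failed

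*SAP*

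**What the plan says.** Outcome has one collection point. For treated episodes, footnote b to Protocol Table 2 gives "duration (assessed at the Week 1 visit) and outcome (assessed at the recurrence FU visit"). The SAP definition of the endpoint (2.1.3.1.3) agrees: "The outcome of the TTP recurrence is assessed at the recurrence follow-up visit and is collected in the eCRF". Table 2 places that visit 7 (±1) days after the end of caplacizumab.

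Protocol 3.4.1.3 deals with a restart of daily PE within an ongoing recurrence period. A new visit cycle begins under Table 2, and for the cycle it replaces, "All remaining visits of the original schedule are no longer applicable and are not to be performed". SAP 1.4 repeats the rule and refers to SAP Table 5.

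The planned analysis is in SAP 2.4.4.4.3: "The outcome of the recurrence at the recurrence follow-up visit will be summarized for each recurrence episode". On the denominator, the same section says "The denominator for the percentage calculation is the number of assessable participants at each time point". SAP 2.4 adds the general rule: "Missing values will not be included in the denominator count when computing percentages". SAP 2.4.4 analyses efficacy as observed, without imputation unless otherwise specified.

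For episodes without caplacizumab, Appendix 1 footnote a collects "duration and outcome (assessed at the recurrence FU visit"), and that visit is 30 days after the end of daily PE.

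**The concern.** Whether an outcome record exists depends on how the course went. A course that holds until its follow-up visit is recorded; a course that ends in renewed daily PE before then has its recording visit removed. Data missing for that reason are informative, and an as-observed percentage is then conditional on not having failed early.

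This bears on the second study objective, safety and efficacy of repeated caplacizumab use. SAP 2.4.4 says the effect of retreatment on recurrence-period endpoints will be evaluated and sets up treated and not-treated groups for those endpoints. The refractory-disease endpoint has also been dropped (SAP 1.6), so the outcome table carries more of the weight in describing unsuccessful courses.

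**Working it through.** The plan gives no figure to reproduce: "The sample size is not based on statistical considerations", and the analysis is descriptive. The check traces one treated course through the rules and then gives an illustration of scale.

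**Tracing an interrupted course**

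1. Caplacizumab and daily PE are given, and daily PE stops. The Week 1 visit, one day after the last daily PE, collects duration.
2. Before the recurrence follow-up visit, daily PE has to be restarted. SAP 2.1.4 runs the recurrence period to the follow-up visit, so this falls within an ongoing recurrence period.
3. A new cycle starts and the first cycle's follow-up visit is not held. Its outcome field stays empty.
4. If the new cycle is a new episode, the first course is not assessable and leaves the denominator. If the cycles form one episode (SAP 2.1.4 speaks of the last recurrence follow-up visit of that episode), the only outcome recorded is the one after re-treatment.
5. No text assigns an outcome to the interrupted course. SAP 2.5.4 Table 1 ends the follow-up period at the recurrence follow-up visit date, which does not exist for that course. The note below the tables covers early termination of the trial only.

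**Scale, as an illustration**

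Let f be the share of courses with a new recurrence before follow-up, and g the share of good outcomes among courses that reach it. The planned table shows g. Over all started courses, with a new recurrence counted as unfavourable, the share is (1 − f) × g.

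- Input for f: Protocol 1.2.4 reports exacerbations in 3 of 36 caplacizumab subjects in TITAN. 3/36 = 8.3% (printed as 8.4%).
- Assumption for g: 90% to 100%; the documents give no value.
- g = 90%: table 90%; all courses (1 − 0.083) × 0.90 = 82.5%; gap 7.5 points.
- g = 100%: table 100%; all courses 33/36 = 91.7%; gap 8.3 points.

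**Early relapses after stopping drug**

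Protocol 1.2.4 also reports 7 TITAN relapses 4 to 10 days after stopping caplacizumab. Spread evenly, that is one per day. A visit on day 6 comes after two of them (days 4 and 5); a visit on day 8 comes after four (days 4 to 7). Then f = (3 + 2)/36 = 13.9% to (3 + 4)/36 = 19.4%. This range needs further assumptions, discussed under the objection.

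**The case against.** The strongest reply is that the failures are not lost. A restart of daily PE meets the SAP definition of recurrence. It is counted in the recurrence summaries (SAP 2.4.4.3) and, as a TTP-related event, per recurrence period (SAP 2.4.4.1). Every exacerbation or relapse is an SAE (Protocol 3.4.9.1). SAP 2.5.3 presents the number of patients with missing data when relevant. Outcome at follow-up is not among the main endpoints in the protocol synopsis, and nothing is formally tested. All of this stands, and it rules out the inference that treatment failures are concealed from the study report. It does not correct the percentage in the outcome table.

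The reply also limits the size of the effect:

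- The restart rule sends patients to the caplacizumab schedule (Protocol Table 2, SAP Table 5). Appendix 1 and SAP Table 6 state no restart or cancellation rule, so loss of outcomes in untreated episodes cannot be read from the text.
- All 7 early TITAN relapsers had ADAMTS13 activity below 10% near the end of treatment. This protocol provides for treatment extension in such patients, so the relapse rate may not carry over. Adding 7 to 3 also assumes that relapsers and exacerbators were different subjects, which is not stated.
- The documents do not define the outcome categories.
- If the new recurrence falls on the day of a scheduled visit, assessments already done need not be repeated (Protocol 3.4.1.3), so a few outcomes may survive.
- Keeping the Week 1 duration of a course that responded and later recurred is not an error. In untreated episodes duration is collected at the follow-up visit together with outcome, so there is no general pattern of favourable data being kept while unfavourable data are lost.

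**Conclusion.** The point holds for caplacizumab-treated episodes. As written, the outcome table omits courses because they were interrupted by a new recurrence, or reports them only after re-treatment. The direction, too favourable, assumes only that such a course would not otherwise be placed in a favourable category.

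The cautious illustration is 8.3% of treated courses dropping out, which is 7.5 to 8.3 percentage points if 90% to 100% of the remaining courses do well. It rests on the TITAN on-treatment exacerbation rate carrying over. The 14–19% range is possible but rests on the extra assumptions named above.

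A reader might go further and apply the placebo exacerbation rate in TITAN, 11/39 = 28.2%, to untreated episodes, concluding that their table would read 100% where about 72% (28/39 = 71.8%) is correct. The documents do not support that: Appendix 1 states no cancellation rule, and neither document defines a success category. What can be said is that the loss may differ between treated and untreated episodes, because their follow-up visits fall at different times and only one schedule carries the restart rule. A comparison based on this table is therefore unsafe.

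The defect is confined to one descriptive table and comparisons drawn from it.

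**What to change.** Change the SAP only:

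- State whether a restarted visit cycle is a new episode or part of the same one, and use that consistently in all per-episode tables.
- In 2.4.4.4.3, use all started courses as the denominator. Add the derived category 'new recurrence (re-initiation of daily PE) before recurrence FU', taken from the recurrence visit dates.
- Show separately the number of courses without a follow-up visit for other reasons, such as death or withdrawal.
- In 2.5.4 Table 1, end an interrupted period the day before the new recurrence visit. Do the same in Table 2 if cycles can restart in untreated episodes, and say whether they can.

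The dates are already collected, so no new visit, eCRF item or change to treatment is needed, and the derivation can be applied to an existing database. The cost is a little programming, and the reported outcome proportion becomes less favourable.
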